10.6.2 Final Clinical Study Report

The final CSR will present the balance of all safety and immunogenicity (if any) data through Day 364 (the scheduled end of trial). The database will be locked and the final CSR prepared, when all of the above data have been entered, reviewed, and all queries related to the data have been addressed. Any decisions to deviate from the planned analyses will be described in detail in the final CSR.

10.7 Computer Methods

Statistical analyses will be performed using SAS[®] version 9.3 or greater under a Windows operating system.

11 TRIAL LEGAL AND ETHICAL REQUIREMENTS

11.1 Compliance with Regulatory Requirements

This trial will be conducted in accordance with the protocol, the Declaration of Helsinki (amended Fortaleza, Brazil, 2013), International Conference on Harmonisation (ICH) GCP Guidelines, and the US FDA regulatory requirements.

11.2 Ethics Committee

This trial will be conducted under the auspices of a properly-constituted IRB, as defined by US regulatory requirements, and in accordance with the Declaration of Helsinki (amended Fortaleza, Brazil, 2013). This committee will review and approve all aspects of the trial, including the protocol and ICF to be used, any and all advertising or informational materials, and any modifications made to the protocol and ICF, prior to, or during the trial. Prior to initiation of clinical activity, investigators will provide Novavax with a copy of the communication from the IRB indicating approval of the protocol and ICF. In the event that a central IRB is used, Novavax will provide copies of correspondence to the investigators. All changes to the protocol or ICF must be reviewed and approved prior to implementation, except where necessary to eliminate apparent immediate hazards to human subjects.

If applicable, the investigators will be responsible for obtaining annual IRB renewal throughout the duration of the trial. Copies of the investigators' annual report to the IRB and copies of the IRB continuance of approval must be furnished to Novavax.

11.3 Informed Consent

The investigators or designated site trial staff members will be responsible for obtaining written informed consent (and any applicable local or state regulatory documentation), signed and dated by each subject, prior to his/her participation in the trial. Informed consent will be obtained from a subject after a full explanation of the purpose of the trial, the risks and discomforts involved, potential benefits, etc, have been provided by the investigators, both verbally and in writing. The original signed copy of the ICF must be maintained in the institution's records and will be subject to inspection by a representative of Novavax and/or regulatory agencies. The subject will also be given a copy of the signed consent form.

11.4 Required Site Documentation

The following documents must be provided to Novavax or its designee prior to the start of the trial:

- Current *Curriculum Vitae* and medical licenses (as applicable) for the principal investigator and all sub-investigators,
- Financial Disclosure Forms from the principal investigator and all sub-investigators,
- Signed protocol and amendments (if any),

Nanoparticle Influenza	Vaccine, Quadrivalent	Confidential	qNIV-E-301 Protocol
Novavax, Inc.	Version 4	.0 – 31 October 2019	Page 65

- Copy of correspondence from the IRB indicating approval of the protocol, ICF, and any site-specific trial advertisements, signed by the IRB chairperson or designee, and containing the name and address of the IRB,
- Membership roster of the IRB, listing names and occupations. If an investigator participating in this trial is an IRB member, documentation should be provided of his/her abstention from voting on this protocol,
- ICF reviewed and approved by the IRB, or a revised document if changes were requested by the committee with the IRB stamp and date, and
- Reference ranges for all safety tests required in the protocol and documentation of laboratory licensure if the trial site's local clinical laboratory will be used.

11.5 Subject Confidentiality

Individual subject medical information obtained as a result of this trial is considered confidential and disclosure to third parties, other than those cited below, is prohibited. Subject confidentiality will be further ensured by utilizing a subject identification code and subject initials. Relevant US national and local jurisdictions governing privacy rules and protection of human subjects will be followed in this trial.

In compliance with regulatory guidelines regarding the monitoring of clinical studies, and in fulfillment of the investigator's obligations to Novavax, it is required that data generated as a result of the trial be available for inspection, on request, by personnel from Novavax, CRO monitors representing Novavax, and/or regulatory agencies. These shall include all trial relevant documentation, including medical histories to verify eligibility, laboratory test results to verify transcription accuracy, treatment and diagnostic reports, and admission/discharge summaries for hospital admissions occurring while the subject is on-trial.

As part of the required content of the informed consent, subjects must be informed that their records will be reviewed by Novavax and/or regulatory agencies. Should access to the medical record require a separate waiver or authorization, it is the investigator's responsibility to obtain such permission from the subject in writing before the subject is entered into the trial.

Concomitant Medications Review ^[2]	X	X	Х	X	Х	X	Х
Subject Diary Review				X ^[3]			
End of Trial							Х

APPENDIX 1 – QNIV-E-301 TRIAL PROCEDURES SCHEDULE

Note: Procedures shaded in grey are performed via scripted telephone call. ^[1] Vital signs to be captured pre-vaccination and between 30 to 60 minutes post-vaccination.

^[2] All adverse events and concomitant medications taken will be collected through Day 28; thereafter, only MAEs, SAEs, and SNMCs and medications taken for these events will be collected.

^[3] The subject diary will be reviewed by the investigator and collected at the Day 28 visit.

^[4] If needed, a physical examination may be performed, based on the investigator's discretion.

^[5] To be collected from a subset of approximately 140 subjects from several pre-designated clinical sites.

APPENDIX 2 – QNIV-E-301 SUBJECT DIARY CARD (DRAFT)

*A subject diary will be provided to all subjects to record solicited and unsolicited adverse events experienced, concomitant medications used, and any medical visits/procedures sought, within the first 7 days following the Day 0 vaccination. The above is a sample excerpt from such a diary. It is provided for informational purposes only and may differ from the actual diary issued to subjects.

APPENDIX 3 – QNIV-E-301 BLOOD DRAW SCHEDULE

Trial Visit Day	Amount of Blood Drawn for Immunogenicity Assessment (mL)	Amount of Blood Drawn for CMI Assessment (mL)
Day 0 (pre-vaccination)	20	27 ^[1]
Day 7 $(\pm 1 day)$		27 ^[1]
Day 28 (±4 days)	20	27 ^[1]
Day 182 (±7 days)	20	27 ^[1]
TOTAL FOR ENTIRE TRIAL (mL)	60 - 168	3 [2]

^[1] To be collected from a subset of approximately 140 subjects from several pre-designated clinical sites.

^[2] Most subjects will provide up to 60 mL of blood in the trial. A subset of approximately 140 subjects from several pre-designated clinical sites will provide up to 168 mL.

APPENDIX 4 – QNIV-E-301 SUBJECT MEASUREMENT TOOL

(Do not use this page in clinic, as it may not be to exact scale)

The Subject Measurement Tool consists of a transparent set of concentric circles with diameters that correspond to the ranges in the toxicity grading scale (2.5, 5, and 10 cm, in diameter). Subjects are instructed to overlay the template over the injection site for any reaction that can be visually observed (eg, redness, swelling, bruising). An assessment of severity is then made by determining the circle that best describes the size of the reaction: reactions that are smaller than Circle A (2.5 cm) are considered Grade 0; reactions larger than Circle A but equal to or smaller than Circle B (5 cm) are considered Grade 1; reactions larger than Circle B but equal to or smaller than Circle C (10 cm) are considered Grade 2; reactions larger than Circle C are considered Grade 3. The table below summarizes the severity grading for visible injection site reactions based on size.

Severity Grade	Injection Site Grading Description
0 - Normal	Reaction size fits inside Circle A
1 - Mild	Reaction size larger than Circle A, but fits inside Circle B
2 - Moderate	Reaction size larger than Circle B, but fits inside Circle C
3 - Severe	Reaction size larger than Circle C

Definition of Severity Grading for Visible Local Adverse Events

APP	PENDIX 1 – QNIV-E-301 TRIAL PROCEDURES SCHEDULE	32
	PENDIX 2 - ONIV-E-301 SUBJECT MEASUREMENT TOOL	

LIST OF TABLES

Table 1:	Trial Design for qNIV-E-301	10
Table 2:	Programmatically-Determined Protocol Deviations	15
Table 3:	Listing of Diary Solicited Events	23
Table 4:	Definition of Severity Grading for Adverse Events	23
Table 5:	Severity Grade Definition for Solicited Gastrointestinal Adverse Events and Fever	24
Table 6:	Decimal Numbers for Parameters	29

LIST OF ABBREVIATIONS

LIST OF ABBREVIATIONS			
Abbreviation or Term	Definition		
AE	Adverse Event		
AESI	Adverse Event of Special Interest		
ANCOVA	Analysis of Covariance		
C	Celsius		
CD	Cluster of Differentiation or Compact Disc		
CDC	Centers for Disease Control and Prevention		
CI	Confidence Interval		
CMI	Cell-Mediated Immunity		
CMO	Chief Medical Officer		
CRA	Clinical Research Associate		
CRO	Contract Research Organization		
CSR	Clinical Study Report		
CTM	Clinical Trial Manager		
CTMS	Clinical Trial Management System		
eCRF	Electronic Case Report Form		
EDC	Electronic Data Capture		
FDA	Food and Drug Administration		
GCP	Good Clinical Practice		
GMR	Geometric Mean Ratio		
GMT	Geometric Mean Titer		
HA	Hemagglutinin		
HAI	Hemagglutination Inhibition		
HEENT	Head, Eyes, Ears, Nose, Throat		
ICH	International Conference on Harmonisation		
IM	Intramuscular		
IP	Investigational Product		
ITT	Intent-to-treat		
IWRS	Interactive Web Randomization System		
LLOQ	Lower Limit of Quantitation		
MAE	Medically-attended Event		
MedDRA	Medical Dictionary for Regulatory Activities		
μg	Microgram		
mg	Milligram		

Abbreviation or Term	Definition
μL	Microliter
mL	Milliliter
μM	Micromolar
mM	Millimolar
MN	Microneutralization
NA	Neuraminidase or Not Applicable
NI	Non-inferiority
NIV	Nanoparticle Influenza Vaccine
nm	Nanometer
NP	Nucleoprotein
PBMC	Peripheral Blood Mononuclear Cell
PD	Protocol Deviation
PP	Per Protocol
PT	Preferred Term
qNIV or Quad-NIV	Nanoparticle Influenza Vaccine, Quadrivalent
SAE	Serious Adverse Event
SCR	Seroconversion Rate
SD	Standard Deviation
Sf	Spodoptera frugiperda
SNMC	Significant New Medical Condition
SOC	System Organ Class
SOP	Standard Operating Procedure
SPR	Seroprotection Rate or Surface Plasmon Resonance
TGS	Toxicity Grading Scale
TMF	Trial Master File
tNIV or Tri-NIV	Nanoparticle Influenza Vaccine, Trivalent
VLP	Virus-Like Particle
WHO	World Health Organization
w/v	Weight to Volume

1 INTRODUCTION

The influenza virus poses a formidable risk of infection resulting in serious illness in older adults. Based on estimates by the Centers for Disease Control and Prevention (CDC), in the US alone, up to 85% of all influenza-related deaths and 70% of all influenza-related hospitalizations occur in people 65 years of age or older [CDC 2017]. During the current influenza season (2018-19), interim estimates indicate that vaccine efficacy in older adults (\geq 50 years of age) remains relatively low at 24% (-15% to 51%) against all influenza types [Doyle 2019].

In light of the continued suboptimal effectiveness of seasonal influenza vaccines, particularly in older adults, Novavax has developed a novel recombinant hemagglutinin (HA) quadrivalent nanoparticle influenza vaccine (Quad-NIV) for the prevention of disease due to influenza virus in adults ≥ 65 years of age, using a recombinant baculovirus and insect cell technology. With a nanoparticle structure, recombinant wild-type sequenced HAs, and use of Matrix-M1 adjuvant, Quad-NIV may offer several important advantages over existing licensed egg-derived seasonal influenza vaccines, including avoidance of antigenic mismatch due to egg-adaptive mutations; induction of both broadly cross-reactive antibody responses against emerging drift variants of seasonal influenza viruses [Shinde 2018]; and potent cross-reactive polyfunctional CD4+ T cells.

In a recent Phase 2, dose-finding, formulation-optimizing trial in adults ≥ 65 years of age, multiple formulations of Quad-NIV, containing HA-based antigens representing the 4 influenza strains recommended for inclusion in the 2018-2019 Northern hemisphere seasonal influenza vaccine [VRBPAC 2018, WHO 2018] and co-formulated with Matrix-M1 adjuvant, given intramuscularly, induced robust hemagglutination inhibition (HAI) antibody responses against both homologous A/B and drifted H3N2 strains. Three formulations in particular: formulation A (60 μg HA of each strain in-clinic mixed with 50 μg of Matrix-M1); formulation B (60 μg HA of each strain co-formulated with 50 µg of Matrix-M1); and formulation C (60 µg HA of each strain co-formulated with 75 µg of Matrix-M1), induced comparable HAI antibody responses (using both egg-propagated or wild-type VLP agglutinins as reagents) against all evaluated homologous and drifted H3N2 strains. In addition, all three formulations outperformed Fluzone HD on HAI antibody responses to all evaluated homologous and drifted H3N2 strains using the wild-type VLP HAI assays, which assessed the binding of vaccine-induced antibodies to HA sequences reflective of circulating viruses not subjected to egg adaptation. The short-term reactogenicity and overall safety profiles (through 182 days of follow-up) of the three formulations were also comparable. Formulation C (60 µg HA of each strain co-formulated with 75 µg of Matrix-M1) induced substantially higher median counts of homologous and drifted strain-specific polyfunctional CD4+ T cells at Day 7 following immunization. Finally, formulation C elicited significantly higher mean hemagglutination inhibition (HAI) titers than unadjuvanted Quad-NIV (formulation E containing only 60 µg HA of each strain) for 5 of 6 tested viral hemagglutinins. The totality of safety and immunogenicity data to date indicate that formulation C of Quad-NIV is the best candidate to advance in further clinical development.

The Phase 2 data warrant confirmation of the non-inferiority of immunogenicity of 240 μg Quad-NIV containing antigens (60 μg HA of each strain) representing the 4 influenza strains

Novavax, Inc.

recommended for inclusion in the 2019-2020 Northern hemisphere seasonal influenza vaccine [VRBPAC 2019, WHO 2019], co-formulated with 75 µg Matrix-M1 adjuvant, as compared to a US-licensed quadrivalent seasonal influenza vaccine comparator, Fluzone Quadrivalent, to generate data to support licensure of Quad-NIV for the prevention of influenza disease in adults > 65 years of age.

1.1 **Study Design**

This is a Phase 3, randomized, observer-blinded, active-controlled trial to evaluate the immunogenicity and safety of 240 µg Quad-NIV co-formulated with 75 µg Matrix-M1 adjuvant against a licensed comparator in clinically stable adults \geq 65 years of age to be conducted in the United States. Approximately 2650 eligible subjects will be enrolled and randomized at a 1:1 ratio into 1 of 2 treatment groups, as shown in Table 1 below. The active group (Group A) and the comparator group (Group B) will each consist of approximately 1325 subjects. Both groups will be stratified by site, age (65 to < 75 and \ge 75 years), and history of prior year receipt of the 2018-19 influenza vaccine. On Day 0, all subjects will receive a study treatment as indicated in Table 1 by intramuscular (IM) injection. Total injection volumes for Quad-NIV will be 0.5 mL. Trial follow-up for each subject will span approximately 1 year from the Day 0 injection. It is anticipated that a percentage of the randomized trial subjects will not complete the trial. Subjects who withdraw or are discontinued will not be replaced.

Table 1: Trial Design for qNIV-E-301

		Day 0 Trial Treatm	ent Injection			
Treatment Group	Vaccine	HA Dose per Strain, μg (H1N1/H3N2/By/By)	Matrix-M1 Adjuvant Dose	Injection Volume	Treatment Arm	Subjects Per Group
A	Quad-NIV	60, 60, 60, 60	75 μg	0.5 mL	Non-dominant	1325
В		2019-20 Fluzone Qu	ıadrivalent ^[1]		Non-dominant	1325
Total Trial Subjects				2650		

Abbreviations: B_V = B Victoria lineage; B_Y = B Yamagata lineage; HA = Hemagglutinin

Note: All subjects will receive a single vaccination by IM injection on Day 0. If the non-dominant arm is not available for injection, then the dominant arm will be used.

1.2 **Randomization and Treatment Assignments**

Subject randomization will be conducted using an Interactive Web Randomization System (IWRS). Stratification will be by site, age, and history of receipt of the 2018-19 influenza vaccine. Proportions of subjects in the various strata will not be pre-specified; rather, the goal will be to achieve an approximately equal distribution of subjects with these characteristics across the two treatment groups.

Preparation and administration of each test article dose will be performed by unblinded vaccine pharmacists/administrators. These persons, identified prior to trial dosing, will not perform any trial assessments post-dosing.

^[1] Fluzone Quadrivalent will be administered at the manufacturer's recommended dose and volume.

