7 ANALYSES ADDRESSING PROTOCOL OBJECTIVES

7.1.1 Analyses of Primary Immunogenicity Objectives

The Per-Protocol (PP) population (ie, randomized subjects who received the assigned dose of the test article according to the protocol, have HAI serology results at Day 0 and Day 28, and have no major protocol deviations) will be the primary population for immunogenicity analysis. A separate intent-to-treat (ITT) population analysis will not be produced unless > 5% of at least 1 treatment group is excluded from the PP population. No missing data will be imputed. For

Version 3.0 - 01 November 2019

GMTs and GMRs, titers reported below the lower limit of quantitation (LLOQ, ie, below the starting dilution of assay reported as "< 10") will be set to half that limit (ie, 10/2 = 5).

For purposes of determining non-inferiority (and exploratory superiority) in immunogenicity of 240 µg Quad-NIV co-formulated with 75 µg Matrix-M1 adjuvant, relative to a US-licensed comparator, Fluzone Quadrivalent, for all Quad-NIV homologous influenza strains (2 influenza A and 2 influenza B strains) at 28 days post-vaccination, derived/calculated endpoints will include:

- Two-sided 95% CIs for the ratio of Day 28 post-vaccination GMTs between Quad-NIV and Fluzone Quadrivalent will be constructed using log normal distribution. The log₁₀ values will be used to construct a CI using the analysis of covariance (ANCOVA) with treatment group and baseline at Day 0 (adjusted for intergroup variation in baseline [pre-vaccination] titers) as the covariates under two-sided type I error rate of 0.05. No type I error rate adjustments will be made. The mean difference and the corresponding CI limits will then be exponentiated to obtain the ratio of GMT and the corresponding CI.
 - A sample SAS code for between-group geometric mean ratio (GMR_{new/ref}) is given below:

```
proc mixed data= fludata;
      by Visit;
      class Treatment;
      model log(HAI 28) = log(HAI D0) Treatment/noint;
      lsmeans Treatment/cl diff e alpha=0.05;
run;
```

- Two-sided 95% CIs for the difference of the SCRs between Quad-NIV and Fluzone Quadrivalent will be based on the Newcombe hybrid score (METHOD = SCORE riskdiff-option for PROC FREQ in SAS).

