- Ratio of GMTs between treatment arms at Day 28 post-vaccination (adjusted for intergroup variation in baseline [pre-vaccination] titers).

An additional time-point at Day 182 may also be tested.

Microneutralization (MN) responses at Days 0 and 28 post-vaccination will include:

- GMT defined as the antilog of the mean of the log-transformed neutralizing titer for a given treatment group.
- GMR defined as the ratio of post-vaccination and pre-vaccination neutralizing GMTs within the same treatment group (designated as GMR_{Post/Pre}).
- SCR defined as proportion of subjects in a given treatment group with either a baseline reciprocal titer of < lower limit of quantitation (LLOQ) and a post-vaccination reciprocal

titer 4-fold higher than the LLOQ, or a baseline reciprocal titer of \geq LLOQ and a post-vaccination reciprocal titer \geq 4-fold higher than the baseline titer.

• Ratio of GMTs between treatment arms at Day 28 post-vaccination (adjusted for intergroup variation in baseline [pre-vaccination] titers).

An additional time-point at Day 182 may also be tested.

The methods for the calculation of GMT, GMR, SCR, and ratios of GMTs for Microneutralization (MN) responses are the same as those for HAI responses.

Analysis of exploratory CMI response endpoints will be performed on a subset of approximately 140 subjects from several pre-designated clinical sites (approximately 70 subjects per treatment arm) and results may be reported as an addendum to the main clinical study report.

The analysis for CMI response may include:

- Counts of Peripheral Blood T Cells characterized based on various cell surface markers at Day 0, 7, 28, and 182.
- Counts and proportion of specific CD4 T cells expressing two and three cytokines in response to influenza hemagglutinin stimulation at Day 0, 7, 28, and 182.
 - The boxplots for counts of two and/or three cytokines may be generated based on log₁₀ scale values.
- GMR ratio of geometric mean of specific CD4 T cells expressing two/three cytokines between Treatment A (Quad-NIV) and Treatment B (Fluzone) at Day 7, 28, and 182.
 - The log₁₀ values will be used to construct a 90% CI using the analysis of covariance (ANCOVA) with treatment group and baseline at Day 0 as the covariates under two-sided type I error rate of 0.10.
 - LLOQ is defined as 1. If counts is zero, it will be set to half that limit to take log_{10} scale (ie, $log_{10}(1/2) = -0.3$).

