12.2 Adjustments for Covariates

Comparison of GMTs between treatment groups will be adjusted for pre-vaccination titer.

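### The HAI, MN and CMI ANCOVAs omit the factors used to stratify randomisation, so their intervals will be conservative to the extent that those factors predict response beyond the Day 0 value

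*SAP*

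**What the plan says.** Randomisation is 1:1. In SAP 1.2, "Stratification will be by site, age, and history of receipt of the 2018-19 influenza vaccine"; the age strata are 65 to <75 and ≥75 years (SAP 1.1). The stated aim is similar distributions of these characteristics in the two arms. Protocol 3.1 and 3.3 agree.

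None of the three factors enters a between-arm model:

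- **HAI GMT ratio (SAP 7.1.1; Protocol 10.4.1.1).** The plan is to "construct a CI using the analysis of covariance (ANCOVA) with treatment group and baseline at Day 0". The sample code has "class Treatment" as its only class variable and the model line "model log(HAI 28) = log(HAI D0) Treatment/noint".
- **General covariate rule (SAP 12.2).** "Comparison of GMTs between treatment groups will be adjusted for pre-vaccination titer". No other covariate is named.
- **MN GMT ratio (SAP 7.2).** It uses the HAI method and so has the same omission.
- **CMI ratio (SAP 7.2).** The plan is to "construct a 90% CI using the analysis of covariance (ANCOVA) with treatment group and baseline at Day 0 as the covariates", in "approximately 70 subjects per treatment arm".

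Neither document gives a stratified sensitivity analysis or a reason for leaving the factors out.

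**The concern.** When randomisation is stratified, the usual practice is to carry the stratification factors into the analysis. Stratification removes most between-arm imbalance on site, age group and prior vaccination, so these factors contribute little to the sampling error of the treatment difference. A model without them does not know this. Whatever they explain beyond the Day 0 value is counted as residual noise, and the standard error is overstated.

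What is at stake is the reported precision of the HAI, MN and drifted-strain GMT ratios, the GMT limb of the exploratory superiority rule (SAP 2.2.3, lower bound above 1.5), and the CMI ratio. The CMI subset keeps the stratified allocation, because every subject at the designated sites takes part (Protocol 6.1.2).

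**Working it through.** **1. The plan's own figures.** For SCR non-inferiority with rates 0.50 and 0.48, margin 0.10, one-sided 0.025 and 97.5% power per strain:

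n = (1.96+1.96)² × (0.50×0.50 + 0.48×0.52) / (0.10−0.02)² = 1200 per arm.

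At 0.9^(1/4) = 97.4% power it is 1190. The stated 1195 is reproduced, and it rests on SCR, not on an ANCOVA.

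For GMT, the margin is log10(1/0.67) = 0.174 and the stated SD is 0.3 to 0.4. Then n = 2×SD²×(1.96+1.96)²/0.174² gives 92 (SD 0.3) or 163 (SD 0.4) per arm. With 1195 per arm, power is about 100%, as the plan says.

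**2. Inputs that the documents do not give.** These are assumptions:

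- R², the residual variance explained by the strata given Day 0: 0 to 0.30.
- CMI log10 SD: 0.5 (0.3 to 0.8 as a range).
- Number of sites in the simulation: 19 for HAI, 4 for CMI.
- HAI residual SD: the stated titer SD of 0.4, which is an upper bound.

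**3. Width.** Half-width = t × SD × √(1−R²) × √(2/n). Adding the strata therefore multiplies the width by about √(1−R²).

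| R² | Relative width | HAI 95% CI around a ratio of 1.0 (n=1195, SD 0.4) | CMI 90% fold half-width (n=70, SD 0.5) |
|---|---|---|---|
| 0 | 1.00 | 0.929–1.077 | 1.38 |
| 0.10 | 0.949 | 0.932–1.073 | 1.36 |
| 0.20 | 0.894 | 0.936–1.068 | 1.33 |
| 0.30 | 0.837 | 0.940–1.064 | 1.31 |

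For CMI SDs of 0.3 to 0.8, the planned fold half-width runs from 1.21 to 1.68.

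**4. Coverage of the planned interval.** With well-balanced strata the limit is 2Φ(z/√(1−R²))−1.

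- 95% interval: 2Φ(1.96/0.949)−1 = 96.1% at R² 0.10, and 98.1% at 0.30.
- 90% interval: 2Φ(1.645/0.949)−1 = 91.7% at R² 0.10, and 95.1% at 0.30.

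Simulated stratified permuted blocks agree in direction and rough size: 97.7% (HAI) and 94.7% (CMI) at R² 0.30. The true SD of the treatment estimate was almost the same with and without the strata, so the excess lies in the reported interval.

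**5. Cost if the strata carry no information.** The simulated CMI half-width at R² = 0 was 0.1403 without the strata and 0.1408 with them, about 0.3% to 0.4% wider. For HAI there was no visible change.

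**6. Decisions.** At SD 0.4, the lowest point estimate that clears 0.67 moves from 0.721 to 0.719 at R² 0.10 (0.713 at 0.30). The lowest that clears 1.5 moves from 1.615 to 1.609 (1.596 at 0.30).

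Power for the GMT superiority limb, with assumed residual SD 0.35 and n = 0.9×1325 ≈ 1192:

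- Reported SE = 0.35×√(2/1192) = 0.01434; true SE at R² 0.10 = 0.01434×0.949 = 0.01360.
- True ratio 1.65: log10(1.65/1.5) = 0.0414. Planned: Φ((0.0414−1.96×0.01434)/0.01360) = 83.6%. With the strata: Φ(0.0414/0.01360−1.96) = 86.1%.
- True ratio 1.60: the same formulas give 49.8% and 54.0%.

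**The case against.** The strongest reply is that the gain is unproven and may be nil. Day 0 titer may already carry much of the age and prior-vaccination effect, and no document says what remains. That stands. A reader might infer that the planned intervals are certainly wider than the design supports; the documents show the omission but not that result.

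Second, no primary decision depends on it. That also stands. SAP Table 6 reports GMT ratios to two decimals, so at R² 0.10 the HAI interval above would print as 0.93–1.07 instead of 0.93–1.08.

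Third, the superiority rule also needs the SCR-difference lower bound above 10%, and the SCR interval is untouched here. The gains in step 6 therefore apply to one limb of a two-limb exploratory rule, and they are shown near the threshold, where power is most sensitive. They are not gains in declaring superiority.

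Fourth, the CMI ratio is descriptive, is listed among analyses that may be done, and has no success criterion. It might seem that CMI must suffer most because it is small and comes from few sites. The documents give no CMI SD, site effect or site count, and the relative gain depends on R², not on n.

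Fifth, simulated coverage for small stratum effects cannot be told apart from nominal. With 1500 runs the Monte Carlo standard error near 95% is √(0.95×0.05/1500) = 0.56 points. Over-coverage is clear only when the effects are large.

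None of this supplies a reason to leave the factors out.

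**Conclusion.** The omission is a documented fact in all three ANCOVAs. Its consequence is conditional. If the strata predict response beyond the Day 0 value, the reported intervals are conservative, and including the strata narrows them by about 2.5% at R² 0.05, 5% at 0.10 and 16% at 0.30. If they do not, there is essentially no change. Every R² value is an assumption.

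A reader might take the mismatch between randomisation and analysis as a threat to validity. It is not one: the treatment estimate is unbiased, the type I error is not inflated, and GMT non-inferiority is unaffected at about 100% power. Any benefit is confined to the precision of the HAI, MN and drifted-strain GMT ratios, the GMT limb of the exploratory superiority rule, and the CMI ratio with about 70 subjects per arm. This is a low-cost efficiency improvement.

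**What to change.** Amend SAP 7.1.1, 7.2 and 12.2 and Protocol 10.4.1.1 before unblinding:

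- Add age stratum and prior-year vaccination as fixed effects to the HAI, MN and CMI ANCOVAs.
- Add site in one stated form: a random effect for HAI and MN, within the PROC MIXED step already planned, and a fixed effect for CMI, where there are only a few sites.
- Use the strata as entered in the IWRS.
- Keep the Day 0-only model as a sensitivity analysis.

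The cost is wording, a few model terms and a few degrees of freedom. No new data are needed. If the sponsor prefers the Day 0-only model as primary, the adjusted model should at least be pre-specified as a sensitivity analysis or the omission justified.
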